8.4.2. Method of Detecting AEs and SAEs

Care will be taken not to introduce bias when detecting AEs and/or SAEs. Open-ended and non-leading verbal questioning of the participant is the preferred method to inquire about AE occurrences.

8.4.3. Follow-up of AEs and SAEs

After the initial AE/SAE report, the investigator is required to proactively follow each participant at subsequent visits/contacts. All SAEs will be followed until resolution, stabilization, the event is otherwise explained, or the participant is lost to follow-up (as defined in Section 7.3). Further information on follow-up procedures is provided in Appendix 3.

8.4.4. Regulatory Reporting Requirements for SAEs

- Prompt notification by the investigator to the sponsor of an SAE is essential so that legal obligations and ethical responsibilities towards the safety of participants and the safety of a study intervention under clinical investigation are met.
- The sponsor has a legal responsibility to notify both the local regulatory authority and other regulatory agencies about the safety of a study intervention under clinical investigation. The sponsor will comply with country-specific regulatory requirements relating to safety reporting to the regulatory authority, institutional review boards (IRBs)/independent ethics committees (IECs), and investigators.
- An investigator who receives an investigator safety report describing an SAE or other specific safety information (e.g., summary or listing of SAEs) from the sponsor will review and then file it along with the SmPC and will notify the IRB/IEC, if appropriate according to local requirements.
- Investigator safety reports must be prepared for suspected unexpected serious adverse reactions (SUSARs) according to local regulatory requirements and sponsor policy and forwarded to investigators as necessary.

8.4.5. Pregnancy

- If a pregnancy is reported, the investigator will record pregnancy information on the appropriate form and submit it to the sponsor within 24 hours of learning of the pregnancy.
- In case of pregnancy, the participant will exit the study.
- While pregnancy itself is not considered to be an AE or SAE, any pregnancy complication or elective termination of a pregnancy for medical reasons will be reported as an AE or SAE.
- Abnormal pregnancy outcomes (e.g., spontaneous abortion, fetal death, stillbirth, congenital anomalies, and ectopic pregnancy) are considered SAEs and will be reported as such.

8.5. ADAb and Serum Drug Level Assessments

Serum samples will be drawn from all participants at all visits. The samples will be sent to the Department of Medical Biochemistry at Oslo University Hospital Radiumhospitalet, Norway, by regular mail or currier with the aim of reaching the laboratory within seven days after the sampling date. Serum TNFi levels and ADAb will be measured using validated automated fluorescence assays. These assays are currently used to assess samples for clinical practice from hospitals throughout Norway and have been used in prior clinical trials (32, 33, 56).

Serum drug levels of SC TNFi are measured using recombinant TNF on the solid phase. As a result, only active TNFi (with the ability to bind TNF) will be measured. The assay for antibodies to TNFi only detects neutralizing antibodies, i.e., antibodies that block the TNF-binding capacity of the TNFi. All assays are fully automated (including dilutions) on the AutoDELFIA platform (PerkinElmer).

8.6. Genetics

A 4 ml blood sample for DNA isolation will be collected from participants who have consented to participate in the study. Analyses using DNA/RNA will assess possible associations between genes and gene expressions and response/immunogenicity. Analyses will only be conducted at a group level and participants will not receive individual feedback/genetic counseling.

Genetic analyses might take place in other countries than Norway including but not limited to the Netherlands, Sweden, Austria, Great Britain, Iceland, and the United States of America. These samples will be handled pseudonymised, the sample will be marked with a study ID. The laboratory receiving the samples will only have access to the study ID. The patient identification list will be stored locally at each site.

Biobank samples will be stored until 31.12.2037 and remaining samples will thereafter be destroyed.

See Appendix 4 for more information regarding genetic research.

8.7. Biomarkers

Biomarker analyses as appropriate to investigate exploratory objectives may be performed.

8.8. Health Economics

For all participants throughout the study, the investigator and study site personnel will collect data about health care resource utilization associated with medical encounters.

The data collected will

- Include the reasons and duration of hospitalizations and emergency room visits and
- Exclude procedures, tests, and encounters mandated by the protocol.

The sponsor may use the collected data to conduct economic analyses.

All participants will be asked to fill in the three standard instruments (questionnaires) to capture work productivity and health related quality of life: SF-36, EQ-5D and WPAI:RA. All questionnaires will be collected by the eCRF module ViedocMe. If the patients do not respond to the questionnaires, two reminders will be sent out. Approved versions of the questionnaires in the primary language of each country will be used.

36-Item Short-form health survey (SF-36)

The SF-36 is a multi-purpose, short-form health survey with 36 questions (57). It yields an 8-scale profile of functional health and well-being scores as well as psychometrically-based physical and mental health summary measures and a preference-based health utility index (SF-6D) (58). It is a generic measure, as opposed to one that targets a specific age, disease, or treatment group. Accordingly, the SF-36 has proven useful in surveys of general and specific populations, comparing the relative burden of diseases, and in differentiating the health benefits produced by a wide range of different treatments (57). See Appendix 14.

European Quality of Life 5 Dimensions (EQ-5D)

The EQ-5D is a utility instrument for measurement of health-related quality of life. Applicable to a wide range of health conditions and treatments, it provides a simple descriptive profile and a single index value for health status (59, 60). See Appendix 15.

Work Productivity and Activity Impairment Questionnaire: Rheumatoid Arthritis (WPAI:RA)

The Work Productivity and Activity Impairment (WPAI) questionnaire is a tool that assesses impairments in both work and daily activities. It consists of six items that determine employment status and measure absenteeism caused by health issues, presenteeism, and overall health-related impairment in both paid work and regular activities over the preceding 7 days. The questionnaire yields four outcomes: i) the percentage of work time missed due to health; ii) the percentage of impairment experienced while working due to health in the past 7 days; iii) the percentage of overall work impairment; iv) activity impairment resulting from health issues. Participants will be asked to answer the Work Productivity and Activity Impairment Questionnaire: Rheumatoid Arthritis V2.0 (WPAI:RA) (61, 62). See Appendix 16.

9. Statistical Considerations

The statistical analyses are planned to be carried out when:

- The planned number of participants have been included
- Each included participant has completed their end-of-study visit, withdrawn, or been withdrawn according to protocol procedures
- All data from the study period have been entered, verified, and validated according to the data management plan

Prior to the statistical analysis, the data will be locked from further entering or editing. A SAP will be finalized prior to any analysis of treatment effects. The SAP will include a more technical and detailed description of the statistical analyses described in this section. This section gives a summary of the planned statistical analyses of the most important endpoints, including the primary endpoint and some key secondary endpoints. The SAP will be finalized, signed, and dated prior to database lock. Any deviation from the original statistical plan will be described and justified in the CSR.

9.1. Statistical Hypotheses

The primary objective is to study whether TDM is superior to standard of care in sustaining disease control during the 18-month follow-up period. To this end, we define the following hypotheses:

- Null hypothesis: The probability of sustained disease control over 18 months in the TDM group equals that in the control group
- Alternative hypothesis: The probability of sustained disease control over 18 months in the TDM group differs from that in the control group.

The null hypothesis will be tested against the alternative hypothesis. Superiority of TDM over standard of care will be claimed if the primary null hypothesis is rejected by a two-sided test using a significance level of 5% and the treatment difference is in favor of the TDM group.

9.1.1. Multiplicity Adjustment

Only a single hypothesis test will be carried out, and only the p value associated with this comparison will be reported. No other hypothesis test will be carried out or p values reported, hence adjustment for multiplicity is not needed. All other comparisons will be descriptive and, where appropriate, accompanied by confidence intervals (unadjusted for multiplicity).

9.2. Analysis Sets

For the purposes of analysis, the following analysis sets are defined:

All efficacy and safety analyses will be carried out in the full analysis set, defined as all randomized participants who have received at least one SC TNFi injection following randomization.

For both efficacy and safety analyses, participants will be included in the analyses according to their randomization group.

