6.1. Study Intervention Administered

6.1.1. The TDM Group

In the TDM, the SC TNFi dose will be adjusted according to the algorithms outlined in Table 1 in order to keep the drug level within the therapeutic range.

Prior to a dose change, the study personnel must check by a phone call to the participant if the drug has been administered according to the treatment algorithm (as defined in Table 1) or if injections have been postponed or dropped due to medical or other reasons.

The following exceptions from the algorithm in Table 1 are recommended if the drug has not been administered according to the treatment algorithm during the last month:

- If the drug level is low with no or low ADAb and there has been a pause in medication of more than 1 week for the last month prior to the blood sampling the dose should be kept stable
- If the drug level is high and the participant has taken the injection in a higher dose or more frequent than prescribed, the dose should be kept stable.

The reason for pause in therapy should be recorded in the eCRF.

In the TDM group, results for drug levels and ADAb will be reported to the investigators via the eCRF within 10 days after receiving the sample. Results in the standard care group will be recorded in the eCRF but not accessible to study personnel, and transferred to the PI upon conclusion of the clinical trial.

Table 1. Study Intervention

	Adalimumab	x	y	z
Trade name(s)	Originator and all approved adalimumab biosimilars*			
Type	Biologic drug			
Dose Formulation	Subcutaneous (SC) injection			
Recommended Dose**	40 mg SC every 14 days, if necessary 40 mg SC every 7 days or 80 mg SC every 14 days			
IMP and NIMP	IMP			
Drug target range	5.0-12.0 mg/L			
Cut-off ADAb high levels	> 50 µg/L			
TDM strategy				
• Within target range	Keep dose			
• Low drug levels, ADAb undetectable or low levels	Decrease dosing interval by one week to a maximum of 40 mg/week			
• Low drug levels, ADAb high levels	Switch to another therapy			
• High drug levels	Increase dosing interval by one week up to a maximum of 6 weeks			

* All adalimumab biosimilars approved by the European Medicines Agency
**According to the Summary of Product Characteristics (SmPC)
ADAb = anti-drug antibodies; TDM = Therapeutic drug monitoring

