6.1.2. The Standard of Care Group

In participants randomized to the Standard of care group, the SC TNFi will be administered according to standard of care without knowledge of serum drug levels or ADAb at all visits throughout the study. Results of serum drug levels and ADAb testing in the Standard of care group will be kept hidden from the investigators.

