6.1.3. Both Groups

In order to identify the primary endpoint, each study center will have a phone number for participants to call in case of increased disease activity. If a participant is experiencing a potential flare, a visit will be arranged within one week after contacting the study center to allow for a clinical examination and documentation of disease status.

Participants with a flare (primary endpoint) will be followed according to the visit scheme. Further therapy will be at the discretion of the treating physician, but for participants in the TDM group, an increase in dose will be recommended if the drug level is low (according to the TDM algorithm).

If SC TNFi is terminated due to any reason, the participant will still be included in the study and followed with study visits according to the planned visit schedule. The reason for termination of therapy should be recorded in the eCRF. If SC TNFi is terminated due to AE, the choice of treatment should be at the discretion of the investigator. Participants who are

switched to another treatment during the study will still be followed according to the visit scheme. Switching between biosimilar drugs is allowed at any time during the study.

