6.3. Assignment to Study Intervention

On the day of enrolment, participants will be assigned a unique randomization number in ascending numerical order at each study site. The randomization number encodes the participant's assignment to one of the two treatment groups of the study according to the randomization schedule. Once a randomization number has been assigned, it may not be reassigned.

Eligible participants will be allocated in a 1:1 ratio between TDM and Standard of care using a permuted block randomization procedure stratified by country (N=3), using random block sizes. Details of block size and allocation sequence generation will be kept in a separate document unavailable to those who enroll participants or assign treatment.

The computer-generated allocation sequence will be incorporated into the eCRF system and made available to site personnel. The allocation will not be available until the participant has signed the informed consent form and deemed eligible to participate in the study. That is, study personnel will only know the treatment allocation of included participants, but not of future participants.

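### The only analysis set (Protocol Section 9.2) requires an SC TNFi injection after randomisation, a condition that the TDM strategy can prevent in one arm only

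*Protocol*

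**What the plan says.** Section 9.2 defines one set and gives it full scope: "All efficacy and safety analyses will be carried out in the full analysis set". That set is "defined as all randomized participants who have received at least one SC TNFi injection following randomization". Participants are then analysed in their randomised group.

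The parts of the protocol that interact with this rule are:

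- **Randomisation (Section 6.3):** "On the day of enrolment, participants will be assigned a unique randomization number".
- **Baseline test (Sections 1.3 and 8.5):** drug level and ADAb are sampled at every visit in all participants, including baseline. Samples are sent to one laboratory "with the aim of reaching the laboratory within seven days after the sampling date".
- **Release of results, TDM arm (Section 6.1.1):** "results for drug levels and ADAb will be reported to the investigators via the eCRF within 10 days after receiving the sample".
- **Action, TDM arm (Table 1):** for low drug level with high ADAb, "Switch to another therapy".
- **Control arm (Section 6.1.2):** "Results of serum drug levels and ADAb testing in the Standard of care group will be kept hidden from the investigators".
- **Follow-up after stopping (Section 6.1.3):** "If SC TNFi is terminated due to any reason, the participant will still be included in the study". Section 7.1 likewise wants participants who stop the intervention kept, where possible, for the primary outcome.

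**The concern.** The trial compares two strategies in people who already use the drug, so the strategy starts at randomisation and not at the next injection. Acting on the baseline ADAb result is delivery of the TDM strategy. Section 9.2 nevertheless makes entry to the analysis depend on a later event that the TDM strategy can prevent and the control strategy cannot.

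No section exempts the baseline result from Table 1, and no second analysis set is defined. Multiple imputation (Section 9.3.2.1) and the missing-data sensitivity analyses (Section 9.3.2.2) deal with missing values inside the set, so they cannot bring back someone outside it. Sections 6.1.3 and 7.1 keep these participants in follow-up but do not change set membership. Their outcomes would be collected and then left out.

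Three things are at stake:

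- **Comparability.** The arms would differ in composition in the trial's only hypothesis test.
- **Information.** Those lost are people on whom the algorithm acts at once. Section 3 plans to study both participants with ADAb and those affected by the algorithm.
- **Safety.** Adverse events after a switch ordered by TDM would be missing from the safety comparison, although assessing the safety of proactive TDM is a secondary objective.

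**Working it through.** **Plan figures.** Section 9.5 assumes 72.5% versus 85% flare-free, at least 350 randomised and 1:1 allocation, hence 175 per arm. The unpooled two-proportion formula at two-sided 5% reproduces its Table 2 entries for the 12.5-point difference: 330 at 80% power and 440 at 90%. The protocol gives no figure for exclusions under Section 9.2, so the rest rests on stated assumptions.

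**When a TDM participant is excluded.** Four conditions must hold together: low level with high ADAb at baseline; result back before the next injection; switch made before that injection; new drug not an SC TNFi.

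**Assumptions (none given by the protocol).** The next injection is uniform over 0–14 days after baseline, 14 days being the standard interval in Table 1. The result is available T days after sampling and the switch is made d days later. A share k is switched to a drug that is not an SC TNFi. A share p of the TDM arm has low level with high ADAb at baseline, taken as 1–5%.

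**Step 1: share of these participants switched before the next injection.** P = max(0, 1 − (T + d)/14).

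| T (days) | d = 0 | d = 3 | d = 7 |
|---|---|---|---|
| 5 | 64% | 43% | 14% |
| 7 | 50% | 29% | 0 |
| 10 | 29% | 7% | 0 |
| 14 or more | 0 | 0 | 0 |

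The turnaround limits add up to 7 + 10 = 17 days, at which P is 0. They are maxima, and no minimum is stated. P is also near 0 if the sample is always taken just before an injection.

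**Step 2: participants excluded = 175 × p × P × k.**

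- Extreme (T = 5, d = 0, k = 100%): 175 × 0.01 × 0.643 = 1.1, up to 175 × 0.05 × 0.643 = 5.6.
- Middle (T = 7, d = 3, k = 50%): 175 × 0.01 × 0.286 × 0.5 = 0.25, up to 1.25 at p = 5%.
- Slower (T = 10, d = 3, k = 50%): 0.06 to 0.31.

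**Step 3: shift in the TDM flare-free estimate.** Let those kept be 85% flare-free and those excluded have rate r. Shift = (excluded/175) × (0.85 − r). All rows use p = 5%.

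| Case | r = 50% | r = 72.5% | r = 85% | r = 95% |
|---|---|---|---|---|
| Extreme, 5.6 excluded (3.2% of the arm) | +1.1 | +0.4 | 0 | −0.3 |
| Middle, 1.25 excluded (0.7% of the arm) | +0.25 | +0.09 | 0 | −0.07 |

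Shifts are in percentage points; a positive shift favours TDM. For example, 0.032 × (0.85 − 0.50) = 0.011.

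**Step 4: scale.** The standard error of the planned difference is √[(0.725 × 0.275 + 0.85 × 0.15)/175] = 4.3 points. The largest middle-case shift is about 6% of that (0.25/4.3), and the extreme is about 26% (1.1/4.3).

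**Step 5: error under no effect.** Suppose both arms are truly 72.5% flare-free, and a share e of the TDM arm with a 50% flare-free rate is removed. The TDM rate becomes (0.725 − 0.5e)/(1 − e). At e = 1% the shift is +0.23 points and the one-sided error in favour of TDM rises from 2.5% to 2.8%. At e = 3%, close to the extreme above, the figures are +0.70 points and 3.5%. If those removed are 70% flare-free, the shift at e = 3% is only +0.08 points.

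**The case against.** The strongest reply concerns size. Samples travel by mail or courier from a three-country trial to one laboratory, and at the stated limits the result arrives after the next 14-day injection. A switch must also be decided, prescribed and dispensed through an ordinary pharmacy, and nothing tells participants to withhold injections while waiting. The d = 0 column is therefore a bound. Section 9.2 names the class, so a switch to another SC TNFi keeps the participant in. Entrants are stable with DAS28-CRP below 3.2, which may make the triggering result uncommon. One injection is enough to qualify, so only the first injection cycle is exposed. All of this stands, and it is why the middle case is about one participant or none. It limits the consequence without removing the defect. Section 6.6 also foresees delayed doses, which would widen the window.

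A second reply is that Section 8.4.1 collects adverse events only from start to stop of study intervention, so events after a switch might be lost whatever the analysis set. This does not defeat the safety point: Section 8.3 has any adverse event during the study reported, and the Schedule of Activities registers adverse events at visits.

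A third is that Sections 6.1.3 and 7.1 do not contradict Section 9.2. That is right in the strict sense, since they govern retention. The tension is confined to the participants described here.

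**Conclusion.** The concern holds. As written, Section 9.2 lets the assigned strategy decide who is analysed, in one arm only, and no other section repairs this. The expected effect on the primary estimate is small, may be zero, and has no known direction: at the assumed 5% prevalence, −0.3 to +1.1 points in the extreme case and −0.07 to +0.25 in the middle case, against a planned 12.5. These figures depend on assumed prevalence, turnaround, switching delay, choice of new drug and prognosis, none of which the protocol supplies. In the ADAb subgroup the cost is mainly lost information if injection timing is unrelated to prognosis. The reason to act is that the condition serves no evident purpose in people already on treatment and is almost free to remove. It should be changed, though it does not threaten the trial.

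**What to change.** In Section 9.2, define the full analysis set as all randomised participants, analysed in their randomised group regardless of any injection after randomisation, and use that set for efficacy and safety. This sets the bias from the exclusion to zero and keeps the planned 175 versus 175.

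The cost is one sentence. Participants who stop or switch SC TNFi already follow the full visit schedule (Sections 4.1 and 6.1.3), so no new data collection is needed and the sample size does not change.

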9.3. Statistical Analyses

9.3.1. General Considerations

Randomization

Allocation Sequence Generation

Eligible patients will be allocated in a 1:1 ratio between TDM and standard of care using a computer randomization procedure stratified by country. Permuted block randomization, with random block sizes of 2, 4, and 6, will be used within each stratum. Details of the allocation sequence generation will be kept in a document unavailable to those who enroll patients or assign treatment.

Allocation Procedure to Randomize Patients

The computer-generated allocation sequence will be imported into the eCRF system and made available as patients are enrolled. A particular allocation will not be unveiled until the patient has been deemed eligible to participate and signed the informed consent form.

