6.4. Masking

This is an open-label study; potential bias will be reduced by the following step:
Blinded assessment of part of the primary outcome (joint count).

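### Section 9.3.1 prints the block sizes that Section 6.3 says are withheld from enrolling staff; concealment is slightly weakened, not broken

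*Protocol*

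**What the plan says.** Section 6.3 describes a "permuted block randomization procedure stratified by country (N=3), using random block sizes" and does not name the sizes. It then states: "Details of block size and allocation sequence generation will be kept in a separate document unavailable to those who enroll participants or assign treatment". It adds that "study personnel will only know the treatment allocation of included participants, but not of future participants", so allocations already made are known to staff.

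Section 9.3.1 describes the same procedure and gives the sizes: "Permuted block randomization, with random block sizes of 2, 4, and 6, will be used within each stratum". It then says: "Details of the allocation sequence generation will be kept in a document unavailable to those who enroll patients or assign treatment". That sentence does not mention block size, so the direct conflict is between 9.3.1 and 6.3.

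Section 6.4 begins "This is an open-label study; potential bias will be reduced by the following step", and the only step listed is blinded joint counting.

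**The concern.** The protocol is the document that site staff work from. A protocol cannot both withhold the block sizes from them and print the sizes a few sections later, and no other section reconciles the two statements.

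Block sizes are withheld because past allocations plus known sizes can show which arm comes next. Several features of this trial would give such knowledge some use:

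- Past allocations are visible, because treatment is open.
- Eligibility includes the treating physician's judgement that treatment should continue (Section 5.1), and screen failures may be rescreened up to twice (Section 5.4), so there is some room over whom to enrol and when.
- One of the two routes to a flare is an unblinded agreement between patient and physician that leads to a major treatment change (Sections 3 and 8.2.2).
- The primary model adjusts for treatment and country only (Section 9.3.2.1), which would not remove selection within a country.

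**Working it through.** The protocol gives no figure for predictability, so there is nothing to reproduce. The check sizes what disclosure adds.

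**Inputs.** From the protocol: sizes 2, 4 and 6 within each stratum (9.3.1); three country strata (6.3); 1:1 allocation (6.3 and 9.3.1); at least 350 participants (9.5). Assumed: each size equally likely; an equal split over countries, 350/3 ≈ 117 per list; and, for the worst case, an observer who sees one whole country list in order from the start.

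**Step 1: does knowing the sizes improve the best guess?** Within any balanced block, the arm that is behind has more places left, whatever the block's size. When the arms are level, the places left are equal. The best guess is therefore always the lagging arm (a coin toss when level), and it needs no knowledge of the sizes. For a block of size k = 2m, the expected number of correct guesses is

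m + 2^(k−1)/C(k, m) − 1/2.

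- Size 2: 1 + 2/2 − 0.5 = 1.500
- Size 4: 2 + 8/6 − 0.5 = 2.833
- Size 6: 3 + 32/20 − 0.5 = 4.100

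The long-run rate is (1.500 + 2.833 + 4.100)/(2 + 4 + 6) = 8.433/12 = 70.3%. Simulated lists of 50 to 350 gave 69.9% to 70.2%, identical for an observer who knows the sizes and one who does not. Disclosure adds nothing to this rate.

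**Step 2: how many allocations become certain?** If the sizes are unknown, none, because a longer block is always possible. If they are known to be 2, 4 and 6, certainty arises only inside a block of 6. With A as the leading arm:

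- AAA can only open a block of 6, so the remaining three (BBB) are certain.
- AABA from a level position fits neither a block of 2 nor one of 4, so the remaining two (BB) are certain.

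Each of the C(6,3) = 20 orderings has probability 1/20, and the pattern may start with either arm. Expected certain allocations per block of 6: 2 × (1/20) × (3 + 2) = 0.5. One block in three has size 6 and the mean block length is 12/3 = 4, so the share is (1/3 × 0.5)/4 = 1/24 = 4.2%. Simulation gave 4.1% for lists of 50 to 350.

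**Step 3: what if sites share a country list?** A site that sees only its own allocations does not know its position in a block. Simulating a list of 117 shared at random, with each site guessing its own lagging arm, gave correct rates of:

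| Sites sharing the list | Correct guesses |
|---|---|
| 1 | 70% |
| 2 | 53% |
| 3 | 52% |
| 5 | 52% |
| 8 | 51% |

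The number of sites per country is an assumption.

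**Step 4: does the block of 2 matter?** The Step 1 formula gives 12.262/18 = 68.1% for sizes 4, 6 and 8. Dropping size 2 in this way lowers the correct-guess rate by about 2 percentage points. With the sizes known, the certain share falls to 2.3% (simulated).

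**The case against.** The strongest reply is that this is a drafting slip with almost no consequence. The trial is multicentre and stratified by country, not site, and nothing in the protocol gives one site a view of another's allocations. The 4% needs such a view, in order, from a person prepared to exploit it. Allocation runs through a central system and is revealed only after consent and confirmed eligibility. Those who approach and consent patients are not the ones actively treating them at the time (Sections 10.1.3 and 10.1.4). All of this stands, and it is why the point is minor.

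It does not remove the contradiction. Section 6.3 names block size among the withheld details, and 9.3.1 discloses it. A country may also have only one or a few sites. The numbering described in 6.3, where "participants will be assigned a unique randomization number in ascending numerical order at each study site", leaves open whether lists in effect run by site; it does not establish that they do.

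Three stronger readings are tempting, and the documents do not support them:

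- That disclosure lifts correct guessing from 50% to 70%. The 70% is a property of short blocks seen in full and is the same when the sizes are hidden.
- That about 14 allocations (4% of 350) will be foreseen. This would need a full ordered view of the list in all three countries.
- That concealment has failed. The sequence itself stays restricted and is released one participant at a time.

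**Conclusion.** The point holds as an inconsistency: the withholding of block size promised in Section 6.3 is undone by Section 9.3.1. Concealment is weakened but not broken. What disclosure adds is at most about 4% of allocations becoming certain. That bound rests on equal probability of the three sizes and on an observer with a complete ordered view of a country list. It is much lower where several sites share a list, and the protocol does not say how many do. No effect on the treatment estimate, type I error or power has been shown, and none is claimed. Severity: minor.

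**What to change.** In Section 9.3.1, replace the sentence that names the sizes with wording that matches 6.3, for example: permuted blocks of randomly varying size within each country, with details held in a separate restricted document.

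Deletion alone does not undo a disclosure already made. Allocations not yet issued should therefore be generated with sizes that are not disclosed. This matters most if a country has one or few sites, and is less pressing if the sponsor confirms that each country list is shared by several sites. Leaving out size 2 is optional, since the gain is small.

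The cost is one edited sentence, a new list for remaining allocations and, if longer blocks are chosen, possibly slightly looser balance within country.
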